[figure not shown]

## Sex Effects on Blood Pressure With Handgrip Training

### Research protocol

This study will be designed as a randomized, controlled, cross-over, repeated measures experiment. Fifty young healthy adult participants (25 males and 25 females) will visit the laboratory three times to perform a fatiguing bout of isometric handgrip exercise before and after both 4 weeks of isometric handgrip training and a no-exercise training condition. Participants will be randomly allocated to the isometric handgrip and the non-exercise training conditions using an online program (<http://www.randomizer.org/>). Participants that start with isometric handgrip training will return to the laboratory after a 4-wk washout, as this duration has been shown to decondition cardiovascular outcomes following training (1–3). To eliminate diurnal variation, each participant will visit the laboratory at the same time of day. Main outcomes in each visit will be measured at rest, during the fatiguing bout of isometric handgrip exercise, and 5, 10, 30, and 60-min post-exercise (see figure and Table 1). These measurement timings are aimed to characterize BP, and the cardiac autonomic and vascular function biphasic responses (4–6). Visits 2 and 3 will take place within 7 days of the last training session.

**Figure 1:** Experimental design, a randomized, controlled, cross-over, repeated measurements study. Abbreviations: CON; control, BRS baroreflex sensitivity, RMSSD, root mean square of

**Table 1** Procedures to be conducted in each visit to the laboratory

Procedures	Time (min)
Rest	15
Measurements	
1) BP, arterial stiffness, cardiac autonomic function	5
2) Brachial endothelial function (FMD)	15
Fatiguing isometric handgrip exercise	~ 3-5
Last isometric contraction	
Measurements	
1) BP, brachial blood flow	
2) Cardiac autonomic function (BRS, RMSSD, HF)	
Post 5 min	
Measurements	
1) BP, arterial stiffness (cfPWV), cardiac autonomic function (BRS, RMSSD, HF)	5
Post 10 min	
Measurements	
1) Brachial endothelial function (FMD)	15
Post 30 min	
Measurements	
1) BP, arterial stiffness (cfPWV), cardiac autonomic function (BRS, RMSSD, HF)	5
2) Brachial endothelial function (FMD)	15
Post 60 min	
Measurements	
1) BP, arterial stiffness (cfPWV), cardiac autonomic function	5
2) Brachial endothelial function (FMD)	15
	Total ~ 100

successive differences; HF, high-frequency power band; FMD; brachial artery flow-mediated dilation, cfPWV; central pulse wave velocity.

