#### Isometric handgrip training intervention and control

Participants will train three days per week at home for 1 month using a reliable and validated digital handgrip dynamometer (DynX, MD System, Inc., Westerville, OH, USA)) in a seated position. The isometric handgrip training protocol will consist of four sets (2 for each hand) of two-min sustained contractions starting at 30% MVC interspersed by 1-min resting periods (a total of 12-min). All training sessions will be remotely supervised via Zoom or phone call by a research team member to ensure compliance with the exercise prescription. Before each training session, MVCs will be re-assessed over three repetitions, each separated by 30-s, to ensure an accurate exercise prescription (13). The highest value will be used to determine the target intensity of the session. In the control/washout conditions, participants will be instructed to maintain their normal daily routines.

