#### Post-intervention visits – isometric handgrip exercise acute bout

All participants will return to laboratory to complete the same acute bout of isometric handgrip exercise detailed in the baseline visit after the isometric handgrip exercise training and respective control.

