#### Study Duration

We foresee that this study will be completed in one year. The estimated duration of individual participation in this study is 2 months and each visit to the laboratory will take approximately 2h.

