### Statistical analysis

Linear mixed models will be used to examine the effects of acute isometric handgrip exercise and training on BP, cardiac autonomic, and vascular function outcomes over time (i.e., aim 1, 2, and 3). These will be fitted with restricted maximum likelihood and applying Satterthwaite's method for approximating degrees of freedom for the F test using R lmerTest package (32). Fixed effects will be set as time, sex, training condition, and the random intercept as each participant. All models' residuals will be checked for normality and homogeneity of

variances using both Shapiro-Wilk and Levene tests, respectively, and through QQ plot inspection using the R performance package (33). Natural logarithm (Ln) transformations will be applied to HRV outcomes, as these are generally not normally distributed, but both transformed and untransformed data will be presented. Linear mixed models will be run with and without possible outliers identified through box plots as observations lying outside the 1.5 interquartile range. Unbiased effect sizes - partial omega squares ( $\omega^2$ ) will be estimated for each fixed effect and interactions terms and interpreted accordingly to the rough benchmarks set by Cohen (34) [small ( $\omega^2 < 0.05$ ), medium ( $\omega^2 < 0.25$ ), and large ( $\omega^2 > 0.25$ ) effects sizes]. Post-hoc comparisons will be performed using the Bonferroni correction, in the presence of significant fixed effects and interactions. MVC, %fat and free fat mass, and physical activity outcomes will be added to all linear mixed models as covariates, whereas resting HR and SRauc will be added to FMD and HRV main outcomes, respectively. In addition, the repeated measures correlation coefficient will be used to test associations between isometric handgrip exercise-induced BP changes before and after the training intervention and of BP with cardiac autonomic and vascular function outcomes (35). Multiple imputation procedures using full information maximum likelihood will only be used in case of a significant amount of missing data on outcomes (>15%) and if missing completely at random, as linear mixed modeling provides robust estimates for small to medium amounts of missingness (36). All statistical analyses will be conducted using R software, version 4.2.3 (37) with a significant level ( $\alpha$ ) of 0.05.

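### In training-first participants the washout appears to double as the no-exercise control, and the plan does not fix the reference visit for each condition, so the training effect can be inflated or diluted

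*Combined protocol and SAP*

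**What the plan says.** The Research protocol section describes a randomized cross-over in which participants "will visit the laboratory three times to perform a fatiguing bout of isometric handgrip exercise before and after both 4 weeks of isometric handgrip training". The sentence goes on to name the other condition, which has no exercise. For one sequence it adds: "Participants that start with isometric handgrip training will return to the laboratory after a 4-wk washout". It justifies the four weeks by citing evidence that cardiovascular training adaptations are lost in that time.

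The section on the training intervention and control gives the training length, "Participants will train three days per week at home for 1 month", and one shared instruction for the untrained time: "In the control/washout conditions, participants will be instructed to maintain their normal daily routines". The section on post-intervention visits says the bout is repeated "after the isometric handgrip exercise training and respective control". Study Duration says: "The estimated duration of individual participation in this study is 2 months".

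On analysis, the Statistical analysis section says: "Fixed effects will be set as time, sex, training condition, and the random intercept as each participant". It names no period, sequence or carry-over term and does not say which visit is the baseline for each condition.

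The Research protocol section also says: "Visits 2 and 3 will take place within 7 days of the last training session".

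**The concern.** A before and an after for each of two conditions makes four readings, but there are three visits, so one visit must serve twice. In control-first participants that is harmless: visit 2 is both post-control and pre-training, and nobody has yet trained. In training-first participants visit 2 is post-training. If it also serves as pre-control, the fading of the training effect between visits 2 and 3 is recorded as the result of control. If it does not, visit 3 must stand as an untrained level, which holds only if the effect has gone by then.

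The same label therefore covers two quantities: an untrained person observed for four weeks, and a trained person detraining for four weeks. At stake is the size of the training effect. If men and women detrain at different rates, the sex-by-training difference, which is the subject of the trial, is affected too.

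**Working it through.** **1. Timeline.** The plan's own figure is two months per participant. Training 4 weeks + one combined washout and control period 4 weeks = 8 weeks; 8/4.345 = 1.8 months, which matches. Training 4 + washout 4 + separate control 4 = 12 weeks; 12/4.345 = 2.8 months, which does not. A new pre-control baseline after a separate washout would also need a fourth visit. The combined period is an inference, but it is the reading that fits the visit count, the duration and the shared instruction.

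**2. Inputs for the bias.** D is the true training effect. The 5 mmHg from the Sample size section is used only as a scale, because it comes from acute responses. c is the fraction of D still present at visit 3; the documents do not give it, so the range is 0 to 1. p is the proportion training-first, assumed 0.5. Expected visit means relative to visit 1, with no period effect:

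| Sequence | Visit 1 | Visit 2 | Visit 3 |
|---|---|---|---|
| Training-first | 0 | D | cD |
| Control-first | 0 | 0 | D |

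**3. Contrasts.**
- Before-after change per condition. Training-first: D − (cD − D) = D(2 − c). Control-first: D − 0 = D. Mean: D(1.5 − c/2).
- Post-training against post-control level. Training-first: D − cD. Control-first: D − 0. Mean: D(1 − c/2).
- As above, but with visit 1 also pooled as untrained. The untrained mean is cD/4, giving D(1 − c/4).
- Visit 2 only, training-first against control-first: D − 0 = D for any c.

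| D = 5 mmHg | c = 0 | c = 0.25 | c = 0.5 | c = 1 |
|---|---|---|---|---|
| Change | 7.5 | 6.9 | 6.25 | 5.0 |
| Level | 5.0 | 4.4 | 3.75 | 2.5 |
| Level, visit 1 pooled | 5.0 | 4.7 | 4.4 | 3.75 |
| Visit 2 only | 5.0 | 5.0 | 5.0 | 5.0 |

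Random-intercept models fitted to simulated data on 4,000 participants agreed with the first three rows to within 0.3 mmHg at c = 0, 0.5 and 1. For general p, change scoring gives D(1 + p(1 − c)), so with p from 0.4 to 0.6 the overstatement at c = 0 is 40% to 60%.

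**4. Sex-by-training.** Under level scoring, equal D and a difference Δc between the sexes produce a spurious difference of D × Δc/2. For D = 5 this is 0.6 mmHg at Δc = 0.25 and 1.25 mmHg at Δc = 0.5.

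**5. Precision.** The standard deviations (SDs) are assumed, not in the documents: 5 mmHg within and 9 mmHg between persons. Completers: 50 × 0.85 = 42.5, taken as 42, or 21 per sequence.
- Crossover level contrast: SE = 5 × √2/√42 = 1.09.
- Visit 2 contrast adjusted for visit 1: total variance 25 + 81 = 106 and correlation ρ = 81/106, so SE = √(106 × (1 − ρ²)) × √(2/21) = 2.05.
- The ratio of the two SEs simplifies to √(2(1 + ρ)), so it lies between 1.41 and 2 for any SDs. Here it is 1.88.
- For the difference between sexes each SE doubles (half the participants per sex, then a difference of two estimates): about 2.2 and 4.1 mmHg.
- With D = 5, the root mean squared error of the crossover is √(1.09² + 0.625²) = 1.26 at c = 0.25 and √(1.09² + 1.25²) = 1.66 at c = 0.5. It reaches 2.05 at c = (2/5) × √(2.05² − 1.09²) = 0.69.

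**The case against.** The plan does not commit to change scoring. It describes one baseline visit and two post-intervention visits, which fits a comparison of post-training with post-control levels. The mixed model contains no change score. The individual-responsiveness analysis does use a pre-to-post change, but for training, whose natural starting point is visit 1 or, in control-first participants, visit 2; that does not produce the inflation. Under level scoring with complete washout the estimate is unbiased, and complete washout is what the plan claims, with citations that cannot be examined here. Figure 1 is not shown and may label the periods and reference visits.

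These points stand, and they rule out two stronger readings. A reader might infer that the training effect is biased however it is analysed, or that 7.5 mmHg is the expected result. The documents support neither: the first overlooks level scoring with full washout, and the second needs a scoring rule that the plan only implies. Nothing in the documents shows that the sexes detrain differently either.

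The objection does not settle the matter. The washout claim protects only the level comparison; under change scoring, complete washout gives the largest error. The wording on measuring before and after both conditions, taken literally, points to change scoring. The text neither fixes the choice nor plans a check of the washout.

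**Conclusion.** The point holds as an unresolved reference visit combined with an unchecked washout, not as a demonstrated bias. With balanced sequences, before-after scoring overstates the training effect by 50% if washout is complete, falling to none if nothing fades. Level scoring is right if washout is complete and understates by 25% at c = 0.5 and 50% at c = 1 (half of that if visit 1 is pooled as untrained). A spurious sex difference is possible but modest under level scoring. All of this rests on the inferred combined period and on a value of c that the documents do not give.

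A reader might also infer that the crossover should give way to the visit 2 comparison. On the assumed figures it should not: the visit 2 estimate is the more accurate only when c exceeds about 0.69. It belongs beside the crossover estimate, because it does not depend on c.

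**What to change.** 1. Confirm and state that in training-first participants weeks 5 to 8 serve as both washout and control, and that visit 2 is never their pre-control value. Prespecify the crossover contrast as post-training against post-control level, adjusted for visit 1 and with a period term.
2. Always report beside it, with no preliminary test for carry-over, the visit 2 contrast of training-first against control-first participants, adjusted for visit 1, overall and by sex. State its precision: under the assumed SDs, SE about 2.0 against 1.1 mmHg overall, and about 4.1 mmHg for the sex-by-training difference (95% interval about ±8). Do not let disagreement between the two estimates decide which one carries the conclusion.
3. Report visit 3 minus visit 1 in training-first participants as a descriptive check on washout only. Setting it against visit 2 minus visit 1 in control-first participants compares eight weeks with four and a third visit with a second, so any residual effect is confounded with period.
4. Reconcile "Visits 2 and 3 will take place within 7 days of the last training session" with the washout sentence. As written it cannot hold for visit 3 of training-first participants, about four weeks after their last session, or for visit 2 of control-first participants, who have not yet trained.

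The cost is plan wording, one extra contrast and one descriptive summary on data already collected. No visit or participant is added.

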## Study intervention

### Baseline visit – fatiguing bout of Isometric handgrip exercise

All participants will rest for 15-min, and then the MVC will be determined based on three attempts, each separated by 30-s, with participants in a supine position. The highest MVC will be used to define the exercise workload (30% MVC). Then, participants will perform a fatiguing bout of unilateral isometric handgrip exercise in the supine position using a digital handgrip transducer intertwined with a data acquisition system (Powerlab 16/35; ADInstruments, BellaVista, NSW, Australia). Participants will use their dominant hand and will hold the isometric contraction until task failure. The failure criteria will be defined as the inability to sustain the contraction force within 5% of the target MCV percentage (i.e., 30%). We chose to set the intensity at 30% MVC as this is the standard target intensity of isometric handgrip exercise protocols (7–9) and no differential BP responses have been reported when different intensities (i.e., 20 vs 30 and 45% MVC) are

used (10–12). Based on previous research, we expect that participants will fatigue within 3 to 5 min (i.e., time to task failure) (12). Participants will receive both visual and auditory feedback to maintain the target exercise intensity throughout the session. The same fatiguing bout protocol will be used before and after the training intervention.

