#### *Blood pressure*

Participants will be asked to wear a non-invasive inflating and deflating finger cuff during all study visits. This will allow beat-to-beat BP to be recorded using finger plethysmography (Finometer; Finapres Medical System, Amsterdam, The Netherlands) before, during, and after isometric handgrip exercise in the supine position. Beat-to-beat BP will be averaged offline over 2 to 5-min using Lab Chart 8 (ADIInstruments, BellaVista, NSW, Australia). Beat-to-beat dynamic fluctuations in BP induced by acute isometric handgrip exercise will be quantified through BP variability indices including spectral methods using the adapted HRV module of Lab Chart 8. This will give insight into sympathetic outflow to blood vessels (14,15).

**Brachial BP** of the right arm will also be measured three times at 1-minute intervals before and after isometric handgrip exercise using an automated blood pressure cuff (HEM-7311-ZSA; Omron Healthcare Co, Ltd, Kyoto, Japan) (16). Measurements will be accepted if they do not differ > 4 mmHg, and the average of the last two will be used for data analysis (16). Mean arterial pressure will be estimated as  $2/3 \text{ DBP} + 1/3 \text{ SBP}$ .

**Central BP** will be assessed via carotid artery tonometry (NIHem, Cardiovascular Engineering Inc., Norwood, MA). Brachial systolic and diastolic cuff BPs will be used to calibrate the peak and trough of the signal-averaged pressure waveforms. Carotid pressure waveforms will be calibrated with diastolic and integrated mean brachial cuff pressure. Central BP is then estimated from the calibrated carotid pressure. Central pulse pressure will be calculated as the difference between the peak and trough of the calibrated carotid pressure waveform.

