### *Cardiac autonomic function*

We will place electrodes directly on the skin of each participant to obtain the ECG trace required to estimate both heart-rate variability and baroreflex sensitivity outcomes.

**Heart rate variability and baroreflex sensitivity:** R-R intervals will be sampled at 1000 Hz frequency to obtain digital R waves digital sequences using the single ECG lead module of PowerLab data acquisition system (ADInstruments, BellaVista, NSW, Australia). All data acquisition and offline analyses will be conducted following the standards of the Task Force of the European Society of Cardiology and the North American Society of Pacing and Electrophysiology (17). Offline heart rate variability (HRV) analyses will be performed over a 2-min time series for each time-point (i.e., baseline, during and 5, 30 and 60 min after exercise) using the HRV analysis module of Lab Chart 8 (ADInstruments, BellaVista, NSW, Australia) (18). Main time-domain indices of interest include the standard deviation of NN intervals (SDNN) – a measure of overall variability, and the root mean square of the sum of the squares of the differences between NN intervals (RMSSD) – a measure of cardiovagal modulation. In addition, non-linear time-domain parameters will be derived from the Poincaré plot, including the vertical deviation that reflects mainly cardiovagal modulation (SD1), the longitudinal deviation (SD2), and the non-linear ratio SD1/SD2 an index of autonomic balance analogous to LF/HF ratio (19). The time-frequency domain analysis will be conducted using the Lomb-Scargle Periodogram, which permits accurate estimation of low (0.04 to 0.15 Hz) and high-power frequency (HF) power bands (0.15 to 0.40 Hz) in absolute and normalized power units during exercise conditions. Cardiac baroreflex sensitivity (BRS) will be estimated via the spontaneous sequence method over 2 min through the Lab Chart 8 baroreflex macro. Briefly, this method identifies ramps where increases in SBP ( $> 1$  mmHg) are coupled with increases of the RR interval ( $> 4$  ms) (linearly correlated) that occur over at least 3 beats (minimum sequence). The minimum acceptable correlation coefficient between SBP and RR interval ramps will be 0.80. Then, baroreflex sensitivity is estimated as the average of all regression slopes between the SBP and RR interval.

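### Exercise-time finger blood pressure is read at the end of a hold of unset length, so its sex and training contrasts can mix pressor response with hold duration

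*Combined protocol and SAP*

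**What the plan says.** The section on the baseline visit ends the bout at task failure, not at a fixed time: "Participants will use their dominant hand and will hold the isometric contraction until task failure". Failure means that force can no longer be kept within 5% of the target, which is 30% of maximal voluntary contraction (MVC). On duration the plan says "we expect that participants will fatigue within 3 to 5 min (i.e., time to task failure"). It adds: "The same fatiguing bout protocol will be used before and after the training intervention".

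Table 1 (Research protocol) has one row for measurements under exercise, labelled "Last isometric contraction". It holds BP, brachial blood flow and cardiac autonomic function. No reading at a fixed minute or at a matched time is listed.

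The Blood pressure section records finger BP before, during and after exercise and states "Beat-to-beat BP will be averaged offline over 2 to 5-min using Lab Chart 8". It does not say where in the bout the window starts or ends. Cuff brachial BP is taken only before and after exercise.

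The Statistical analysis section states "Fixed effects will be set as time, sex, training condition, and the random intercept as each participant". Its covariates for all models are MVC, body composition and physical activity. Time to failure is not among the outcomes in Study main outcomes, the fixed effects or the covariates.

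**The concern.** During a sustained contraction BP is expected to climb, so a reading at the end depends on how fast it rises and on how long the person holds. The plan fixes relative force but leaves duration free. The MVC covariate describes strength, not hold time.

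Training could slow the rise and also lengthen the hold, and the two would then offset each other in a reading at failure. A sex difference in endurance would enter the sex contrast in the same way.

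The Sample size section names the effects of training on acute BP responses as an aim, and Research protocol lists the bout as a measurement time for the main outcomes. A null result at the exercise time point could then mean no effect of training, or an effect offset by a longer hold. Without an analysis of time to failure, the reader could not tell which. The planned repeated-measures correlations of exercise-induced BP changes may inherit the same ambiguity.

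**Working it through.** **Inputs from the documents.** Expected hold of 3 to 5 min, a ratio of 5/3 = 1.67 between longest and shortest. One exercise BP row, at the last contraction. An averaging length of 2 to 5 min without an anchor. The plan gives no calculation for exercise-time BP, so there is no figure of its own to reproduce.

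**Assumptions (not in the documents).** BP rises linearly at b = 5, 8 or 10 mmHg/min. Baseline hold T0 = 4 min, the middle of the stated range. Training slows the rise by a fraction c and lengthens the hold by a fraction e.

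**Formulas for the training effect.**
- At the common time T0: -c × b × T0.
- At failure: b × T0 × [(1 - c)(1 + e) - 1].

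With c = 0.20 (mmHg):

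| Reading | Factor | b = 5 | b = 8 | b = 10 |
|---|---|---|---|---|
| Common time, 4 min | -0.80b | -4.0 | -6.4 | -8.0 |
| At failure, hold unchanged | -0.80b | -4.0 | -6.4 | -8.0 |
| At failure, hold +10% (4.4 min) | -0.48b | -2.4 | -3.8 | -4.8 |
| At failure, hold +25% (5.0 min) | 0 | 0 | 0 | 0 |
| At failure, hold +40% (5.6 min) | +0.48b | +2.4 | +3.8 | +4.8 |

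The effect cancels when e = 1/(1 - c) - 1, which is 11%, 25% and 43% for c = 10%, 20% and 30%. This does not depend on T0 or b. The 40% row ends beyond the plan's 5 min. From a 3-min baseline, the same lengthening gives 4.2 min, inside the range.

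**Does averaging remove the problem?** This depends on the anchor, which is not given.
- Mean over the whole bout: half the end value under a linear rise, so every entry halves. The common-time effect is -2.0 to -4.0, against -1.2 to -2.4 at +10% and 0 at +25%.
- Last 2 min before failure: the mean equals the value 1 min before the end. At +10% this is b × (0.8 × 3.4 - 3) = -0.28b, or -1.4 to -2.8. At +25% it is b × (0.8 × 4 - 3) = +0.20b, or +1.0 to +2.0. The same window ending at 4 min in both bouts gives b × (0.8 × 3 - 3) = -0.60b, or -3.0 to -6.0.
- A fixed window from minute 1 to 3 in both bouts: -0.2 × b × 2 = -0.40b, or -2.0 to -4.0, whatever the hold time.

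A 5-min window cannot fit in a 3-min bout.

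**Sex contrast.** With the same rise in both sexes, a gap of d min in mean hold time shifts the reading at failure by b × d. An assumed half-minute gap gives 2.5 to 5 mmHg.

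**The case against.** **Equal effort is a legitimate basis.** The plan deliberately uses a fatiguing bout at a relative load, and comparing people at failure matches effort. This stands, but the plan does not state that choice. A contrast at failure answers a different question from one at equal exercise time, so it should be kept and labelled.

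**The reading may not be terminal.** The same Table 1 row holds autonomic indices that need 2 min of data ("Offline heart rate variability (HRV) analyses will be performed over a 2-min time series for each time-point"), so it is not a single instant. This also stands: that the window ends at failure is the natural reading of the row label, not an explicit statement. The documented gap is the missing anchor. Windows that end at failure or span the bout still vary with hold time; a fixed early window would not.

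**Hold time may not change.** The post-intervention visits repeat the baseline bout. If MVC is re-measured there, which the text implies but does not state, the load follows current strength and limits lengthening of the hold due to strength. With no change in hold time nothing is hidden.

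**Readings that go too far.** A reader might multiply the 2-min width of the stated range by 8 to 10 mmHg/min and call 16 to 20 mmHg the bias. The documents do not support that. The range is an expected spread across participants, not a gap between sexes or a shift after training, and one slope for everyone is assumed. A reader might also set such figures against the plan's 5 mmHg difference. The Sample size section takes that figure from a study of BP after acute handgrip exercise, so it is no benchmark for the rise during a hold.

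**Conclusion.** The point holds for the exercise time point in beat-to-beat finger BP. The bout runs to failure, the window is not anchored and time to failure is not analysed, so the contrast there can mix response with duration.

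The illustrated distortion ranges from none (hold unchanged), through full cancellation (a 20% slower rise with a 25% longer hold), to a reversed sign (a 40% longer hold). It rests on assumed linear rises of 5 to 10 mmHg/min and an assumed training effect. Without failure times by sex or condition, neither size nor direction can be stated: the plan can mask an effect, but the documents do not show that it will.

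A reader might infer that all BP contrasts by sex and training are compromised. They are not. Only one of the five BP rows in Table 1 is read under exercise. Resting and 24-h BP are unaffected. Recovery readings are not taken at failure, though a longer hold could reach them through exercise dose. The change is worth making before analysis because it is cheap.

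**What to change.** In the Blood pressure and Statistical analysis sections:

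1. Pre-specify the length and anchor of the exercise BP window, and name the reading that forms the exercise level of the time factor.
2. For the training contrast, add a matched-time (isotime) reading: the same window in each bout, ending at the participant's shortest failure time among the bouts completed. This keeps participants with a missed visit usable.
3. For the sex contrast, add a fixed early window that all participants reach, with a rule for anyone who fails sooner.
4. Keep BP at failure as a separately labelled equal-effort measure.
5. Report time to failure by sex and condition as an outcome. Do not make it a routine covariate, because training may change it.
6. State whether MVC is re-measured at visits 2 and 3.

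**Cost.** For finger BP this is wording and one extra analysis, since the signal is already recorded throughout. The isotime value lies below the peak response, and it compares one bout at its end with others that are still submaximal. It does not correct recovery readings; reporting time to failure only makes differences in dose visible there. Brachial blood flow, in the same Table 1 row, is not covered by this change.
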